### **Analysis Plan:**

There will be 2 arms to this study: laparoscopic supracervical hysterectomy and sacrocolpopexy with Restorelle® Y mesh and vaginal hysterectomy and sacrocolpopexy using the Restorelle® Dual flat mesh.

We determined that 30 subjects in each arm were needed to detect a difference of 30 minutes or more (standard deviation 30 minutes) in surgical time between the two groups with 80% power and a significance level of .05. We will account for potential subject drop out and loss to follow-up as well as unforeseen factors in recruiting and will plan to recruit 35 subjects to each arm, for a total of 70 subjects.

All statistical analyses will be done using jmp 14. We will use descriptive statistics to show our demographic and baseline data: categorical variables will be presented as n/N (%) with 95% confidence intervals and continuous variables will be presented as mean+/- SD [range]. The two types of hysterectomy (laparoscopic supracervical and vaginal) will be compared. With a continuous outcome and two categorical independent factors, a two-way analysis of variance will be used to evaluate differences between the groups. The results will be presented in a standard ANOVA table, which should be sufficient to determine if differences exist. A linear regression will be done to demonstrate actual changes in surgical time attributed to each variable.

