**Hypothesis:** There is no clinically difference in surgical time in patients undergoing vaginal hysterectomy versus laparoscopic supracervical hysterectomy at the time of sacrocolpopexy

**Study Design:** Randomized trial

**Primary Outcome:** Surgical time defined as time of incision to time of sacrocolpopexy completion (abdominal incisions closed)

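### The sample-size figures do not fit together: on the stated inputs 80% power needs 17 per arm, and 30 per arm gives about 97%.

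*Combined protocol and SAP*

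**What the plan says.** The primary outcome is continuous: "Surgical time defined as time of incision to time of sacrocolpopexy completion (abdominal incisions closed"), in minutes. The whole justification of the trial's size is in the second paragraph of the Analysis Plan. It reads "We determined that 30 subjects in each arm were needed to detect a difference of 30 minutes or more (standard deviation 30 minutes") and continues "in surgical time between the two groups with 80% power and a significance level of .05". The allowance for losses follows as a separate step: "We will account for potential subject drop out and loss to follow-up as well as unforeseen factors in recruiting", after which the investigators "will plan to recruit 35 subjects to each arm, for a total of 70 subjects".

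For the analysis, the next paragraph says that "a two-way analysis of variance will be used to evaluate differences between the groups". The second factor is not named. The plan does not give the test behind the sample size, its sidedness, a drop-out rate or a source for the SD.

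**The concern.** A difference equal to one standard deviation is large, and trials planned to detect it at 80% power are usually much smaller than 30 per arm. The stated number therefore looks too high for the stated inputs. Either one of the five figures is not the one used, or 30 was chosen as a margin that the text does not disclose.

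This is the only support for the trial's size, and it concerns the primary outcome. A reader cannot tell whether 30 minutes was really the planning SD, and so cannot tell how much power the trial has. The stated hypothesis expects no clinically relevant difference in surgical time. A null result can be interpreted only if the reader knows what difference the trial could have detected, and the sentence as written gives the wrong answer to that.

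**Working it through.** **Inputs, all from the Analysis Plan.** Difference δ = 30 min; SD σ = 30 min; α = .05 (sidedness not stated, two-sided assumed first); power 80%; equal arms; stated n = 30 per arm.

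**Step 1. Try to reproduce the 30.** The standardised difference is d = δ/σ = 30/30 = 1.

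- Normal approximation: n = 2(z₀.₉₇₅ + z₀.₈₀)²/d² = 2 × (1.960 + 0.842)² = 15.7, so 16 per arm.
- Exact noncentral t: n = 16.71, so 17 per arm. Power is 78.1% at 16 and 80.7% at 17.
- One-sided .05, exact: n = 13.10, so 14 per arm.

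The stated 30 is not reproduced. It is 30/17 = 1.76 times the required number, or 76% more.

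**Step 2. Power at the stated size.** The noncentrality parameter is d√(n/2).

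- n = 30: √15 = 3.873; power 96.8% (normal approximation 97.2%).
- n = 35: √17.5 = 4.183; power 98.5%.

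**Step 3. Look for another reading that gives 30.** Results are per arm, at d = 1.

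| Reading | Required n |
|---|---|
| Two-way ANOVA, main effect of arm, 80% | 17 |
| Two-sided α = .025, 80% | 21 |
| Two-sided α = .01, 80% | 26 |
| Two-sided α = .05, 90% | 23 |
| Two-sided α = .05, 95% | 27 |
| Two-sided α = .01, 90% | 32 |
| Rank test, 80% | 18 to 20 |
| Equivalence, assumed margin 30 min, true difference 0, one-sided .05 | 18 |
| Equivalence, as above, one-sided .025 | 22 |
| 2×2 interaction of 30 min, 80% | about 64 |

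The ANOVA row supposes that the second factor explains no variance, which is the least favourable case. With total N = 34, the noncentrality is 34 × 0.25 = 8.5 on 30 error df, and power is 80.5%. None of these readings gives 30, and those that change α or power also contradict the stated figures.

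Drop-out does not explain it, because it is applied to the 30 and not included in it: 1 − 30/35 = 14.3%.

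**Step 4. Which single change would give 30.** At n = 30 and 80% power, two-sided .05, the detectable d is 0.7356.

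- Keeping SD 30: 0.7356 × 30 = 22.1 min.
- Keeping 30 min: 30/0.7356 = SD 40.8 min.
- Keeping both: power of about 97%, as in Step 2.

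These are back-calculations, not values in the documents.

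**Step 5. Sensitivity to the SD.** Power at 30 per arm for a 30-minute difference, two-sided .05. Only SD 30 is in the plan; the others are an assumed range.

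| SD (min) | 25 | 30 | 35 | 40 | 45 | 50 |
|---|---|---|---|---|---|---|
| Power | 99.5% | 96.8% | 90.4% | 81.5% | 71.9% | 62.8% |

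**The case against.** The best defence is that the mismatch is on the safe side. Thirty per arm does give at least 80% power for 30 minutes or more, the plan does not say that 30 is the exact minimum, and a cautious round number is a legitimate choice. Surgical time is recorded on the day of surgery, so later loss to follow-up does not erode the primary data. Power falls below 80% only if the SD exceeds about 41, and no such value is in the documents. The hypothesis of no clinically relevant difference could also be read as an equivalence aim, for which a difference test is the wrong calculation.

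Much of this stands. On the plan's own figures the trial is not under-powered, and the larger SDs are only an illustration. It does not rescue the sentence. The plan presents 30 as the number required for 80% power, and 17 would do. A deliberate margin has to be stated, and none is. The equivalence reading gives 18 or 22, not 30; the plan states no margin, and its sample-size sentence is about detecting a difference. One qualification is accepted: the plan does name a test for the analysis, so what is missing is the test behind the sample size.

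**Conclusion.** The concern holds. For a 30-minute difference, SD 30 and two-sided .05, 80% power needs 17 per arm; the stated 30 gives 96.8% and the 35 to be recruited gives 98.5%. A one-sided test widens the gap. The calculation assumes equal arms, equal variances and roughly normal surgical times.

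It is a defect of reporting and justification. If the SD of 30 is correct, the trial has more power than it claims, and the 80% detectable difference is about 22 minutes. The documents do not show which input is off, or whether 30 was deliberately conservative. The point should be corrected, but it does not threaten the primary comparison on the stated inputs.

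**What to change.** Check the records of the original calculation first. If they show a different SD, difference, power or α, correct that input in the sentence. If the stated difference and SD are right, restate the result, for example: *30 evaluable subjects per arm give 97% power to detect a 30-minute difference in surgical time (SD 30 minutes, two-sample t-test, two-sided .05), and 80% power to detect about 22 minutes.* If 30 was chosen as a cautious number, say so. In every case name the test, its sidedness and the source of the SD.

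Keep 30 evaluable and 35 recruited per arm. The cost is one sentence in the Analysis Plan; enrolment, design and analysis do not change.

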**Inclusion Criteria:**

- Age  $\geq$  18, who are to undergo laparoscopic sacrocolpopexy for uterovaginal prolapse and desire concurrent hysterectomy at the time of surgery
- Other concomitant laparoscopic or prolapse and anti-incontinence procedures (cystocele repair, rectocele repair or mid-urethral sling procedures) will be performed at the primary surgeon's discretion.
- Patient's must have an up-to-date PAP smear on record, or a PAP smear is performed in the office and verified to be normal pre-enrollment

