**Randomization**

All subjects will be predetermined by their surgeon to undergo a laparoscopic sacrocolpopexy. The participants will then be randomized to either concurrent vaginal hysterectomy or laparoscopic supracervical hysterectomy according to a computer-generated randomization schedule with the use of the SAS statistical software package (SAS Institute, Cary, NC).

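### Surgical time is to be analysed by a two-way ANOVA although only one two-level factor is randomised, and the ANOVA table called sufficient cannot show whether a clinically relevant difference has been excluded

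*Combined protocol and SAP*

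**What the plan says.** The Hypothesis statement reads "There is no clinically difference in surgical time in patients undergoing vaginal hysterectomy versus laparoscopic supracervical hysterectomy". No margin is attached to it. The Randomization section describes a single allocation: "The participants will then be randomized to either concurrent vaginal hysterectomy or laparoscopic supracervical hysterectomy". No stratification variable is named.

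The Analysis Plan gives 30 per arm as the number "needed to detect a difference of 30 minutes or more (standard deviation 30 minutes) in surgical time between the two groups". Power is set at 80%, the level at .05, and recruitment at 35 per arm.

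For the comparison itself, the Analysis Plan identifies only hysterectomy type, supracervical or vaginal, as the thing to be compared. It then names the method: "With a continuous outcome and two categorical independent factors, a two-way analysis of variance will be used to evaluate differences between the groups". Neither of the two factors is identified in that sentence. On reporting, it relies on an ANOVA table and regards that table as enough to settle whether the groups differ. A further step is announced last: "A linear regression will be done to demonstrate actual changes in surgical time attributed to each variable". The variables meant are not listed.

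The only 95% confidence intervals mentioned in the plan are for categorical variables in the demographic and baseline description.

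**The concern.** A two-way ANOVA needs two factors, and this design supplies one. Mesh product cannot be the other: Surgical Interventions and the Analysis Plan tie the Y mesh to the supracervical arm and the dual flat mesh to the vaginal arm, so mesh and hysterectomy type are the same contrast. If some other factor is meant, its identity and the presence or absence of an interaction are left to be settled later, possibly with the data in view.

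The second issue is whether the output answers the question. The hypothesis is that no clinically relevant difference exists. An ANOVA table carries an F statistic and a p-value. It does not say which arm was slower, by how many minutes, or which differences remain compatible with the data. A non-significant result could then be reported as confirming the hypothesis without anyone showing what had been excluded.

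**Working it through.** **Inputs.** Difference 30 min, SD 30 min, alpha .05, power 80%, 30 per arm needed and 35 per arm recruited (all from the Analysis Plan). A two-sided test is assumed, because sidedness is not stated. An SD of 40 and margins of 20 and 15 min are assumptions, used only to show the range.

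**The plan's own figure.** The normal approximation gives n = 2 × (1.960 + 0.842)² × (30/30)² = 15.7, so 16 per arm; the exact t-test gives 17. The stated 30 per arm is therefore not reproduced and exceeds what its inputs need. At 30 per arm, power for 30 min is about 97%, and 80% power would correspond to an SD of about 41 min. That discrepancy is a separate matter. It matters here only because lack of power at the stated inputs is not the problem, and because an SD near 40 is worth including in the range.

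**Precision of the arm difference.** Half-width of the 95% CI = t(.975, 2n−2) × SD × √(2/n).

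- n = 35, SD 30: 1.995 × 7.171 = 14.3 min.
- n = 30, SD 30: 2.002 × 7.746 = 15.5 min.
- n = 35, SD 40: 1.995 × 9.562 = 19.1 min.
- n = 30, SD 40: 2.002 × 10.328 = 20.7 min.

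**What p>.05 leaves open.** At p = .05 the observed difference equals the half-width, so the far limit of the interval is twice the half-width:

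| Per arm | SD 30 | SD 40 (assumed) |
|---|---|---|
| 35 | 28.6 min | 38.2 min |
| 30 | 31.0 min | 41.3 min |

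**How often the interval settles the question.** These are simulated trials with a true difference of 0, a true SD of 30 and the SD estimated in each trial. By construction p>.05 occurs in 95% of them. The whole 95% CI lies inside the margin in:

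| Margin | 35 per arm | 30 per arm |
|---|---|---|
| ±30 min | 97% | 94% |
| ±20 min (assumed) | 57% | 44% |
| ±15 min (assumed) | 10% | 4% |

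Among the trials with p>.05 at 35 per arm, the CI lies inside ±30 min in 99.4% if the true difference is 0, in 97.5% if it is 10 min and in 95.0% if it is 15 min. At 30 per arm with a true difference of 0, the figure is 97.2%.

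**What the table hides.** Take 35 per arm, SD 30 and an observed difference of 12 min. Then F = (12/7.171)² = 2.80 and p = .099, with CI 12 ± 14.3 = −2.3 to 26.3 min. An observed −12 min gives the same F and p, with CI −26.3 to 2.3 min. Conversely, an observed 15 min gives 15 ± 14.3 = 0.7 to 29.3 min: significant, yet wholly within 30 min. The p-value and the clinical question can diverge in either direction.

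**The regression.** Its variables are not listed. Adhesiolysis over 45 min is among the data recorded during the procedure, and the Summary of tasks places randomisation on the day of surgery, so this finding arises after allocation. Each extra patient in one arm with 45 min of adhesiolysis moves that arm's mean by 45/35 = 1.3 min; adjusting for adhesiolysis would take that out of the arm effect.

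**The case against.** Four points can be made for the plan, and each has some force.

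**The test is probably sound.** The preceding sentence compares only the two hysterectomy types, so two groups is the natural meaning. With two groups a one-way ANOVA is the two-sample t-test. A reader might infer that an invalid analysis would be run or that power would be lost; the documents do not support that. Even a genuine balanced second factor would leave power for the arm effect at about 97% with 60 patients. What stands is that the text does not say which model is meant.

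**An estimate is not wholly absent.** The regression would probably give a signed arm coefficient in minutes, so it would be wrong to say that no difference would be estimated. What stands is that the coefficient is not tied to the primary comparison, the variables are not listed and no interval is stated.

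**At the planned SD and full recruitment, p>.05 does most of the work.** It would overstate the case to say that a non-significant result generally leaves 30 min open: at SD 30 and 35 per arm it almost always excludes that difference. Surgical time is also recorded on the day of surgery, so loss to follow-up should hardly reduce the numbers. The gap matters mainly if about 30 per arm are analysed, if the SD is larger, or if less than 30 min is clinically relevant. The hypothesis gives no margin that would rule out the last.

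**Adjustment for later events is not stated.** A reader might infer that the arm effect will be adjusted for post-randomisation variables. No section says so. Concomitant procedures "will be performed at the primary surgeon's discretion", but that does not say when the decision is made, and a sling or colporrhaphy may be planned before allocation. The caution is firm only for findings made in theatre, such as adhesiolysis.

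**Conclusion.** The point holds as one of specification and reporting. The named method does not match a design with one randomised two-level factor, and the output called sufficient cannot on its own support a hypothesis of no clinical difference.

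The practical harm is moderate. Under the planned SD, the arm difference would be known to within about ±14.3 min at 35 per arm or ±15.5 min at 30. A bare p>.05 is nearly adequate for a 30-min difference at 35 per arm, less so at 30 per arm (limit up to about 31 min), and inadequate if the SD is nearer an assumed 40 (limit about 38 min at 35 per arm) or if a smaller difference matters. These figures assume roughly normal times, equal SDs and a two-sided 5% level. The change should be made; nothing here shows that the trial's primary test would be invalid.

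**What to change.** Replace the two-way ANOVA sentence with one pre-specified comparison of surgical time by randomised arm, analysed as randomised, using a two-sample t-test or a linear model with arm only. Make the mean difference in minutes (vaginal minus laparoscopic supracervical) with its 95% CI the primary result. Judge the hypothesis from that interval against a difference stated before data are seen. The plan's own 30 min is one candidate, but it was set as a difference to detect, so the investigators should either adopt it explicitly as the margin or state a smaller one that they consider relevant.

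Keep findings that arise during surgery, such as adhesiolysis over 45 min, out of the model for the arm effect. List the variables of the planned regression and label it descriptive. Where arms are compared on PFDI-20, ISI and PISQ-12, adjust for the preoperative score already collected.

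The cost is analysis-plan wording only: no new data, no extra patients and no change to any procedure.

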### **Data Collection & Management:**

Preoperative data will include the following:

- Patient age, race, vaginal parity, menopausal state, BMI, comorbid conditions, tobacco use, preoperative prolapse stage, preoperative use of vaginal estrogen
- PFDI-20, ISI, PISQ-12

Data points recorded during the procedure will include:

- Total OR time = operating room time of entry and exit
- Surgical time = time from incision to end of sacrocolpopexy (abdominal incisions closed)
- Total Case time = time from incision to end of procedure
- Hysterectomy time = time from start of hysterectomy to end of hysterectomy
- Concomitant procedures
  - Lysis of Adhesions >45 min
  - Anterior colporrhaphy
  - Posterior colporrhaphy
  - Perineorrhaphy
  - Midurethral sling
  - Other
- Estimated blood loss
- Intraoperative complications
  - Vascular Injury
  - Cystotomy
  - Ureteral Injury
  - Bowel Injury - small bowel, large bowel, rectal

Postoperative data will include the following: 6, 12, 24 months

- POP-Q exam (performed by a provider who did not perform the surgery)
- Vaginal exam, inspection for mesh exposure
- PFDI-20, ISI, PISQ-12
- Assessment of use of postoperative vaginal estrogen

- Review of electronic medical record (inpatient notes, d/c summary, ER visits), assessing for postoperative complications
  - Reoperation for immediate complications = reoperation within 30 days of surgery
  - Abdominal Wound infection = fascial, subcutaneous, cutaneous infection requiring antibiotic treatment
  - Hematoma = intrapelvic/abdominal
  - Vaginal cuff cellulitis/Pelvic Abscess = requiring IV/PO antibiotic therapy and/or transvaginal, transgluteal or percutaneous drainage
  - DVT/PE = diagnosed with Doppler US or CT scan
  - Reoperation for SUI with pubovaginal sling (synthetic or fascial), colposuspension, injection with periurethral bulking agents
  - Reoperation for mesh exposure
  - Reoperation for recurrent POP
  - Bowel Injury/Bowel Obstruction = enterotomy, perforation, ileus, partial/complete obstruction
  - Port site or incisional hernia
  - Need for any radiologic imaging
  - Lower urinary tract injury = bladder, ureteral
  - Neurologic Injury = brachial plexus, abdominal wall (ilioinguinal, iliohypogastric), lower extremity (femoral, sciatic, common peroneal)
  - Pulmonary complications = pneumonia, pulmonary hypertension, pulmonary edema within 14 days of surgery
  - Cardiac = ACS, MI, HF within 14 days of surgery
  - Postoperative ICU admission

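### The primary ANOVA has an unnamed second factor, and BMI and prolapse stage, both recorded before randomization, are in no prespecified model; one named ANCOVA would fix this at almost no cost (minor).

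*Combined protocol and SAP*

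**What the plan says.** - **Outcome.** The Primary Outcome is surgical time, from incision until the abdominal incisions are closed. The Hypothesis is that there is no clinical difference between the arms.
- **Deciding test.** Analysis Plan: "With a continuous outcome and two categorical independent factors, a two-way analysis of variance will be used to evaluate differences between the groups". The plan expects the ANOVA table to be enough to settle whether a difference exists. It does not name the second factor.
- **Further model.** A linear regression is then to show how much surgical time is attributable to each variable. The variables are not listed, and the regression is not made the test of the arms.
- **Baseline data.** Data Collection & Management lists as pre-operative items: "Patient age, race, vaginal parity, menopausal state, BMI, comorbid conditions, tobacco use, preoperative prolapse stage, preoperative use of vaginal estrogen". The Summary of tasks table puts demographic data and POP-Q at the pre-operative visit and randomization on the day of surgery.
- **Randomization.** The section describes a computer-generated schedule and names no stratification factor.
- **Sample size.** "We determined that 30 subjects in each arm were needed to detect a difference of 30 minutes or more", with "standard deviation 30 minutes", "with 80% power and a significance level of .05"; 35 per arm are to be recruited.

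**The concern.** Because the second factor is unnamed, the primary model is not fully specified. It could be chosen after the data are seen, and the candidates include items recorded during surgery, such as prolonged lysis of adhesions, which arise after randomization. The test also takes categorical factors only, so BMI could enter it only in grouped form.

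If BMI and stage predict operating time, leaving them out keeps explainable variation in the error term. Nothing in the design balances them between arms, so any chance imbalance adds to the uncertainty of the estimate. What is at stake is the width of the interval for the arm difference, which matters when the hypothesis is that no clinically relevant difference exists.

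**Working it through.** **Inputs from the Analysis Plan:** difference 30 min, SD 30 min, 80% power, alpha 0.05 (sidedness not stated; two-sided assumed), 30 per arm. **Assumed:** R², the share of within-arm variance in surgical time explained by BMI and stage. The documents give no value, so a range is shown.

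**1. The plan's own figure.** n per arm = 2 × [SD × (1.960 + 0.842) / difference]² = 2 × (2.802)² ≈ 15.7, so 16 (17 with the t distribution). The stated 30 per arm does not follow from the stated inputs. It exceeds the requirement, so it does no harm to power; that discrepancy is a separate matter. At 30 per arm, power for 30 minutes is 96.8% (t) or 97.2% (normal).

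**2. Unadjusted interval at 30 per arm.** SE = 30 × √(2/30) = 7.746 min. Half-width = t(58 df) × SE = 2.0017 × 7.746 = 15.5 min. (At 35 per arm: 14.3 min.)

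**3. Adjusted interval.** With N = 60 and k = 2 covariates (BMI linear; stage linear or two-level), the expected SE ratio is √[(1 − R²)(N − 3)/(N − k − 3)] = √[(1 − R²) × 57/55]. The half-width is 2.0032 (t, 56 df) × 7.746 × ratio. The equivalent gain in patients is 1/ratio² − 1.

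| Assumed R² | SE ratio | Change in SE | Equivalent patients | Half-width (min) |
|---|---|---|---|---|
| 0 | 1.018 | +1.8% | −3.5% | 15.8 |
| 0.05 | 0.992 | −0.8% | +1.6% | 15.4 |
| 0.10 | 0.966 | −3.4% | +7% | 15.0 |
| 0.20 | 0.911 | −8.9% | +21% | 14.1 |
| 0.30 | 0.852 | −14.8% | +38% | 13.2 |

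Power for 30 minutes, using these SEs and 56 df, is 97.0%, 97.6%, 98.7% and 99.4% at R² of 0.05, 0.10, 0.20 and 0.30: a rise of less than 3 points.

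**4. Chance imbalance.** At 30 per arm the standardized difference in a baseline covariate has SD √(2/30) = 0.26. An imbalance of that size moves the unadjusted estimate by about 0.26 × 30 × √R²: 2.4 min at R² 0.10 and 4.2 min at R² 0.30.

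**5. Bearing on the hypothesis.** The plan states no equivalence margin. If 30 minutes is taken as the margin (an assumption), the unadjusted interval lies within ±30 when the estimate is within ±(30 − 15.5) = ±14.5 min. At R² 0.30 this widens to ±(30 − 13.2) = ±16.8 min.

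**The case against.** A reader might infer that BMI and prolapse stage are excluded from the analysis. The documents do not show this:

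- Stage is ordinal and could be the unnamed second factor; BMI could be that factor in grouped form.
- The regression can take continuous BMI, and since its variables are unlisted it may already include the arm and both covariates. The result in minutes would in any case come from the regression, not from an ANOVA table of F tests.

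Both points stand. They turn exclusion into lack of prespecification, and they do not supply a named model with the deciding role.

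A reader might also infer bias or too little power. Neither is supported. Randomization makes the unadjusted comparison valid, its interval already allows for chance imbalance, and power for 30 minutes is about 97%. With a 30-minute margin (assumed) and no true difference, the unadjusted interval would fall within ±30 about 94% of the time by the normal approximation: 14.5/7.746 = 1.87 standard errors.

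Finally, no passage says that BMI or stage predicts surgical time, or that either matters more than site or surgeon. This stands: the choice of covariates is a judgement and the gain cannot be derived from the documents. Against it, the adjustment costs little if the covariates prove weak (about 2% on the SE).

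**Conclusion.** The point holds as a minor one. The deciding test has an unnamed second factor and cannot take continuous BMI, and neither BMI nor pre-operative stage is prespecified in any model, although both are available before randomization. A single ANCOVA is a better primary analysis from data already collected.

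The benefit is a narrower interval and protection against choosing the model after the data are seen; it does not correct a bias. Its size rests on an assumed R² of 0.05 to 0.30, the stated SD of 30 minutes read as the unadjusted within-arm SD, 30 analysed per arm, and two covariate degrees of freedom. The 15.5-minute starting point also assumes no second factor in the model; a useful second factor would already take up part of the gain.

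**What to change.** In the Analysis Plan, before any analysis by arm:

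1. Make the primary comparison the arm coefficient, in minutes with its 95% confidence interval, from one ANCOVA of surgical time on randomized arm, BMI (continuous) and pre-operative prolapse stage (linear or two-level, stated in advance).
2. State that nothing arising after randomization, such as lysis of adhesions or other intraoperative items, is a covariate in this model.
3. Keep the unadjusted difference with its 95% interval as a sensitivity analysis.
4. Let this model replace the two-way ANOVA as the deciding analysis. If the regression is kept for description, list its variables.

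The cost is analysis-plan wording and two degrees of freedom. No new data, visits or patients are needed. A stage variable with more categories would cost slightly more degrees of freedom.
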